Exploring the role of tryptophan metabolites in pediatric migraine

2023.05.01

1. Research objectives, study content and key questions to be addressed

1.1 Research objectives This research focuses on the key scientific issues of "tryptophan metabolites and childhood migraine", and explores the pathogenesis, diagnosis, treatment, and prevention of childhood migraine by combining clinical characteristics and medical history and other multi-level data, with the aim of establishing an assessment system for early identification and intervention of childhood migraine, systematically developing an individualized treatment and assessment system for childhood migraine, and conducting clinical translational research in the field of childhood migraine. We aim to establish an assessment system for early identification and intervention of childhood migraine, systematically carry out individualized treatment and assessment system for childhood migraine, and conduct clinical translational research in the field of childhood migraine. The following are the details: The aim of the study is to establish a system for the early identification and intervention of migraine in children, and to systematically develop an individualized treatment and evaluation system for migraine in children.

1.2 Research content

1.2.1 Exploration of the pathogenesis of migraine in children For the subjects included in the study, blood was collected at any time during the first 2-4 hours of the headache attack in migraine patients; blood was collected at least 24 hours before and after the inter-episode period without headache attack in migraine patients. In healthy controls, blood was collected in a quiet state. Tryptophan metabolite levels were measured by ELISA. The plasma levels of tryptophan metabolites were analyzed in different groups according to the collected medical histories, and the plasma levels of migraine patients were compared with those of healthy controls by t-test: one-way ANOVA was performed between different types of migraine: correlation analysis was performed between the frequency, duration, severity and two types of migraine attacks; logistic regression was performed to screen for possible factors. The results of the above analyses were combined to explore the pathogenesis of migraine in children and to lay the foundation for the improvement of the diagnosis of migraine in children and the development of new drugs.

1.2.2 Exploration of specific diagnostic indexes for migraine in children For the subjects included in the study, blood was collected at any time during the first 2-4 hours of the headache attack in migraine patients, and blood was collected at least 24 hours before and after the headache attack in the inter-episode period in migraine patients. Tryptophan metabolite levels were measured by ELISA. The ROC curve was used to analyze the diagnostic value of the combined diagnosis of tryptophan metabolites, and tryptophan metabolites, and the area under the curve (AUC) of tryptophan metabolites and the combined diagnostic indexes of both were subjected to independent sample t-test to analyze whether there was a statistical difference between the three, and the diagnostic test evaluation indexes were used to evaluate the combined diagnosis of tryptophan metabolites, and tryptophan metabolites respectively, and to evaluate them as The possibility and accuracy of the

specific diagnostic index of migraine in children were evaluated.

2. The proposed research method, technical route, experimental protocol and feasibility analysis.

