2.1.3 Study method

(1) The trial was reviewed by the Research Ethics Committee of Qilu Hospital of Shandong University. Patients were obtained from the pediatricoutpatient clinic of Qilu Hospital of Shandong University, with written permissionfrom parents or guardians and, where appropriate, consent from the children. Theinvestigators were responsible for design, data collection, analysis, and interpretation. Data were collected by field researchers. and all data were confidential for theduration of the trial; trialists and data analysts could not communicate data with eachother. Eligible healthy children and children with migraine were recruited in the first step and basic information about the children and headache characteristics were obtainedby the site staff, and blood was retained from the study subjects for Elisa assay, respectively.

(2) Method for determination of tryptophan metabolite content:

①Timing of blood collection

In the case group, blood was collected at any time during the first 2-4 hours of themigraine attack; in the inter-migraine attack group, blood was collected at least 24hours before and after the headache-free period. In the healthy control group, bloodwas collected in a quiet state.

②Storage and testing methods

5 ml of elbow venous blood was collected from patients and healthy children inpurple tubes, and the samples were immediately transferred to ice-cold glass tubescontaining a mixture of anticoagulant and protease inhibitor, and centrifuged at 3000rpm for 5 minutes at 4°C. The supernatant was stored at -80°C, and tryptophanmetabolite levels were measured by ELISA, and the case and control groups were compared and analyzed.

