2.1.4 Data analysis

Statistical analysis was performed using SPSS26.0 software analysis, and statisticaldata were tested for normality, and the mean standard deviation ($x + S$) was used formeasurement data that conformed to the normal distribution, and one-way ANOVAwas applied for comparison between the three groups, and t-test for two independentsamples was used for comparison between two groups. The correlation between theplasma levels between migraine attacks and the duration of the disease was analyzedby SPSS26.0 correlation analysis.

(1) After completing the questionnaire survey, the researchers collected data

and analyzed the risk of migraine in children due to the interaction of multiple factors, and used logistic regression to screen the indicators related to the risk of migraine in children due to the interaction of multiple factors, and established an early assessment model of migraine in children to achieve early detection, early diagnosis and early prevention of migraine in children.

(2) Based on the collected medical history, different group analyses were performed, and the plasma levels of tryptophan metabolites in migraine patients were compared with those in healthy controls by t-test; one-way ANOVA was performed on the plasma levels of tryptophan metabolites between different types of migraine; correlation analyses were performed between the frequency, duration, severity and two types of migraine attacks; and logistic regression was performed to screen for possible influences on the risk of migraine in children. Logistic regression was performed to screen the factors that may influence the diagnosis of migraine in children.

(3) To analyze the diagnostic value of tryptophan metabolite and tryptophan metabolite combined diagnosis by ROC curve, and to analyze whether there is any statistical difference between the three diagnostic indexes by independent sample t-test, and to evaluate the diagnostic indexes of tryptophan metabolite and tryptophan metabolite combined diagnosis by diagnostic test, and to evaluate the diagnostic indexes of tryptophan metabolite and tryptophan metabolite combined diagnosis as the possibility and accuracy of specific diagnostic indexes for migraine in children were evaluated.

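### The independent-sample t-test named for comparing the AUCs of two single metabolite indexes and their combination is not a valid test for AUCs that, as far as the SAP shows, come from the same children

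*SAP*

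**What the plan says.** SAP section 1.2.2 describes a ROC analysis of the tryptophan metabolites singly and combined. The quantities to be compared are "the area under the curve (AUC) of tryptophan metabolites and the combined diagnostic indexes of both". The test follows at once: "the combined diagnostic indexes of both were subjected to independent sample t-test to analyze whether there was a statistical difference between the three".

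Section 2.1.4, item (3), plans the same analysis, again by ROC curve, and again "to analyze whether there is any statistical difference between the three diagnostic indexes by independent sample t-test". It does not repeat the word AUC.

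On the origin of the measurements, section 2.1.3 says that "5 ml of elbow venous blood was collected from patients and healthy children" and that "blood was retained from the study subjects for Elisa assay". It does not describe separate sets of children for different metabolites.

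The SAP names no paired or correlated-ROC method, and it does not say how the combined index is formed.

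**The concern.** An independent-sample t-test compares the means of a variable in two separate groups of subjects. The comparison here differs in three ways.

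1. **No sample of AUCs.** An AUC is a single summary of all cases and controls. Each index yields one estimate with a standard error; no child has an AUC of their own.
2. **Three quantities.** A two-sample test does not compare three indexes, and the SAP does not say which pairs are meant.
3. **No independence.** The indexes appear to be measured in the same children, and the combined index contains the single ones. Their AUC estimates therefore share sampling error.

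The shorter wording in section 2.1.4(3) leaves another opening. An analyst could run the t-test on the marker values themselves, which would compare concentrations and say nothing about accuracy.

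At stake is the comparative question of section 1.2.2: whether the combination diagnoses migraine better than one metabolite. As written, the SAP would give no valid p-value for it.

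**Working it through.** **Nothing to reproduce.** The SAP states no sample size, AUC or correlation for this analysis. Points 1 and 2 above need no numbers. The figures below size point 3 on assumed inputs, for the nearest test that can be computed: a z-test of the AUC difference that treats the AUCs as independent.

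**Formula.** Let both AUCs have variance V and let their estimates correlate at r.

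- Correct (paired): SE² = V + V − 2rV = 2V(1 − r)
- Covariance ignored: SE² = 2V
- SE ratio (ignored / correct) = 1/√(1 − r)
- True size of the nominal 5% test = 2[1 − Φ(1.96/√(1 − r))]
- Power where the paired test has 80% (mean z = 1.96 + 0.84 = 2.80) = Φ(2.80 − 1.96/√(1 − r))

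At r = 0.5, √0.5 = 0.707, so the SE ratio is 1.41 and 1.96/0.707 = 2.77. The size is 2[1 − Φ(2.77)] = 0.6% and the power is Φ(0.03) = 51%.

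| AUC correlation r | SE ratio | True size | Power (paired = 80%) |
|---|---|---|---|
| −0.4 | 0.85 | 9.8% | 87% |
| 0 | 1.00 | 5.0% | 80% |
| 0.3 | 1.20 | 1.9% | 68% |
| 0.5 | 1.41 | 0.6% | 51% |
| 0.7 | 1.83 | 0.04% | 22% |
| 0.8 | 2.24 | 0.001% | 6% |

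**Which correlations are plausible?** For single versus combined, simulation with normally distributed markers and an equal-weight sum (weights fixed in advance, both single AUCs 0.70, 100 cases and 100 controls) gave mean AUC correlations of about 0.49 to 0.84 as the marker correlation went from −0.4 to 0.5. Even negatively correlated markers gave a positive AUC correlation, because the sum contains the single marker.

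**Power in that contrast** (100 cases, 100 controls, two-sided 5%, 3000 replicates or, against the 0.75 marker, 2000). The true combined AUC follows from Φ([Φ⁻¹(AUC₁) + Φ⁻¹(AUC₂)]/√(2(1 + ρ))), where ρ is the marker correlation. For AUCs of 0.70 and 0.75 with ρ = 0.3 this is Φ((0.524 + 0.674)/1.612) = Φ(0.743) = 0.77.

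| Single AUCs | ρ | Combined AUC | Compared with | Covariance ignored | Paired (DeLong) |
|---|---|---|---|---|---|
| 0.70, 0.70 | 0 | 0.77 | either marker | 19% | 70% |
| 0.70, 0.70 | 0.3 | 0.74 | either marker | 1% | 43% |
| 0.70, 0.75 | 0.3 | 0.77 | the 0.70 marker | 14% | 86% |
| 0.70, 0.75 | 0 | 0.80 | the 0.75 marker | 7% | 50% |
| 0.70, 0.75 | 0.3 | 0.77 | the 0.75 marker | 0% | 15% |

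**Two single markers.** With both AUCs 0.75, 100 per group and marker correlations of −0.4, 0, 0.5 and 0.8, the rejection rate under no difference was 7.7%, 5.5%, 0.9% and 0.0% with covariance ignored. DeLong gave 4.8%, 5.3%, 5.2% and 4.7%. Only a negative correlation produced excess false positives.

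**t-test on raw values.** For two independent markers with equal AUC 0.75 and mean levels 0.5 SD apart, compared in 100 cases, the test rejects 94% of the time although accuracy is identical.

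**The case against.** - **The same-children point is inferred.** This stands, and so does the related point that the SAP gives a blood volume, not a number of draws. It also does not say whether attack and between-attack samples come from the same children. But a combined index can be computed only where both measurements exist, so correlation between single and combined does not depend on those details.
- **Two single indexes is a reconstruction.** The translated text does not name the two metabolites. The reading rests on the words for both and for three. It is the natural reading, and the test would be just as unsuitable for another set of AUCs.
- **The figures describe a z-test that the SAP does not name, on assumed inputs.** True. They are illustrations. The named test cannot be computed on AUCs at all, which is the more basic fault.
- **Comparing with the weaker marker flatters the fix.** This is fair: against the 0.75 marker with ρ = 0.3, the paired test reaches only 15%. The gain there is just 0.77 − 0.75 = 0.02. The covariance-ignoring test still does worse, at 0%.
- **The raw-value reading is unlikely, because section 1.2.2 names the AUC.** Probably so. The 94% only shows what the looser wording of section 2.1.4(3) would allow.
- **The work is exploratory and the error is mostly conservative.** For single versus combined it costs power and does not create false claims. That limits the harm, but the SAP offers no other test for this comparison, and a missed gain from combining would be a wrong answer to its own question.

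**Conclusion.** The concern holds. The named test is wrong as written in both sections: there are no AUC samples to compare, three indexes are not two groups, and the AUCs of a single index and of a combination containing it are not independent. The SAP contains no valid alternative, so it has no valid p-value for whether the combination is more accurate than one metabolite.

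If the test is carried out as a z-comparison without covariance, the expected consequence is lost power: from 80% to 51% at an AUC correlation of 0.5 and to 6% at 0.8. Excess false positives (9.8% at a correlation of −0.4) could arise only between two single markers with negatively correlated AUCs. All these figures depend on assumed sample sizes, AUCs and correlations; the conclusion does not. The individual ROC curves and the diagnostic accuracy measures are unaffected. This should be corrected before analysis.

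**What to change.** In sections 1.2.2 and 2.1.4(3):

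1. Replace the independent-sample t-test with a paired comparison of correlated AUCs, by DeLong's method or a bootstrap that resamples children.
2. Report each pairwise AUC difference with a 95% confidence interval, and name the contrasts in advance, including combined versus each single index.
3. Say in section 2.1.4(3) that the quantity compared is the AUC, so that the two sections agree.
4. State in the same sentence how the combined index is formed. If it is a logistic model fitted to the same children, test its added value with a likelihood-ratio test against the single-marker model and report an optimism-corrected combined AUC. In a simulation with both single AUCs 0.70 and marker correlation 0.5, the optimism was 0.020, 0.016 and 0.006 with 30, 50 and 100 children per group.

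The cost is a change of wording in two places and a few lines of code. No new data are needed. If the combination is fitted on the same children, its corrected AUC may come out slightly lower.

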2.1 Experimental protocol

2.1.1 Inclusion and exclusion criteria of study subjects

Case group inclusion criteria:(1) Age 4-18 years old, male and female are not limited. (2) Meet the diagnostic criteria of ICHD-3 with aura, without aura, and chronic migraine. (3) Migraine was diagnosed by two or more specialized neurologists. (4) PedMIDAS score > 11 (5) Migraine had never been treated (6) Patients and families gave informed consent to the study purpose, significance, risks, benefits, and informed consent. Source: Department of Pediatrics Outpatient and Inpatient Unit, Oilu Hospital. Shandong University

Inclusion criteria for the control group:(1) Age 6-18 years, male and female. (2) Did not meet the diagnostic criteria of ICHD-3 migraine and other headaches. (3) Physical health allowed their participation in the study. (4) Patients and their families gave informed consent to the study purpose, significance, risks, benefits, and information of the study. Source: Department of Pediatrics Outpatient and Inpatient Unit, Oilu Hospital. Shandong University.

Exclusion criteria:

(1) presence of drug overdose (2) autoimmune diseases (3) neurological diseases other than migraine, intracranial masses (4) congenital or hereditary diseases (5) diabetes, bronchial asthma, cardiovascular diseases, pulmonary diseases (6) other types of primary and secondary headache.

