2.1.2 Data collection

(1) Data sources: questionnaires, outpatient medical records and auxiliary examination results.

(2) Collection methods: questionnaire survey, medical records review, blood collection.

(3) Data composition: Basic personal information, migraine triggering factors, clinical features of headache, medication, past medical history, ancillary examinations, and blood samples were collected from all enrolled headache patients.

① Basic personal information included name, gender, age, height, weight (calculated BMI) cultural level, residence address, and contact information.

② Migraine triggering factors: genetic factors, endocrine (menstruation), diet (cheese, chocolate, puffed food), psychological factors (sleep, anxiety, depression, emotional stress, etc).

③ Clinical characteristics of headache included: whether the patient was in the attack phase or inter-attack phase, the location of the patient's headache, the nature of the headache, the degree of pain (assessed using the visual analog scale VAS Appendix), the duration of the disease (years), the frequency of the headache, the duration of each headache, the time of the last pain, the presence of aura, aura symptoms, concomitant symptoms (photophobia, phonophobia, nausea, vomiting, gastrointestinal

symptoms),exacerbation and remission. The information of each headache, duration of last pain,presence of aura, aura symptoms, concomitant symptoms (photophobia, photophobia.nausca, vomiting, gastrointestinal symptoms), aggravation and relief factors, familyhistory, etc.

④Also record medication use, past medical history, ancillary test results such asroutine blood, liver function, kidney function, lipids, blood glucose, ECG, TCD, headCT,head MRIhead MRA examination,etc.PedMIDAS scale score, migraine treatment efficacy assessment scale, headachediary

⑤5ml of venous blood

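### Cases may be 4-18 years old but controls only 6-18, and neither the case-control t-test nor the ROC analysis accounts for age

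*SAP*

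**What the plan says.** Section 2.1.1 sets two age ranges. Cases: "Age 4-18 years old, male and female are not limited". Controls: "Inclusion criteria for the control group:(1) Age 6-18 years, male and female". No reason is given for the difference.

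The case-control comparison is stated twice. In 1.2.1, "the plasma levels of migraine patients were compared with those of healthy controls by t-test"; in 2.1.4(2), "the plasma levels of tryptophan metabolites in migraine patients were compared with those in healthy controls by t-test". Neither place names a covariate, matching or strata.

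The diagnostic analysis in 2.1.4(3) reads "To analyze the diagnostic value of tryptophan metabolite and tryptophan metabolite combined diagnosis by ROC curve". Like its counterpart in 1.2.2, it has no age adjustment and no age limit.

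The only multivariable method is in 2.1.4(1) and (2). The investigators "used logistic regression to screen the indicators related to the risk of migraine in children" and build an early assessment model. Age is not named in that model, and the model is not linked to the t-test or the ROC curve.

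**The concern.** A case-control contrast isolates migraine only if the groups are otherwise comparable. Here the eligibility rule makes the groups differ in age: every child aged 4-5 in the comparison is a case. If a metabolite rises or falls with age, the t-test attributes that to migraine, and the AUC counts youth as diagnostic signal. The document does not say whether the metabolites vary with age.

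Two consequences do not depend on sample size or on the strength of the age relation:

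- With no control under 6, specificity at ages 4-5 cannot be estimated at all, although the stated aim is early identification.
- Any model that keeps the cases aged 4-5 must extrapolate the control age trend below age 6.

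**Working it through.** **Text check.** Sections 1.1 to 2.1.5 contain no age matching, age strata, age covariate or sensitivity analysis limited to the common age range. The SAP gives no sample size, power or effect size, so there is no stated figure to reproduce.

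**Illustration.** From the document: the age limits 4-18 and 6-18. Assumed: no true migraine effect; metabolite linear in age with correlation r = 0.1, 0.3 or 0.5; equal groups of 50 or 100; two-sided 5% level; the same age mix above 6 in both groups; a share p of cases aged 4-5.

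1. Ages. Controls uniform from 6 to just under 19: mean (6 + 19)/2 = 12.5, SD 13/√12 = 3.75. The cases aged 4-5 have mean age 5; the other cases are distributed as the controls.
2. Mean age gap = p × (12.5 − 5) = 7.5p. If ages are spread evenly over 4 to just under 19, then p = 2/15 = 13.3%, the gap is 1.0 year and the case SD is 15/√12 = 4.33.
3. False shift = r × gap / age SD, with the case SD giving the low end and the control SD the high end. For p = 13.3% and r = 0.5: 0.5 × 1.0/4.33 = 0.115 to 0.5 × 1.0/3.75 = 0.133.
4. AUC under no true effect = Φ(shift/√2). For a shift of 0.133: Φ(0.094) = 0.538.
5. Rejection rate of the 5% t-test, from the noncentral t with noncentrality shift × √(n/2). For a shift of 0.133 and n = 100: 0.133 × √50 = 0.94, giving 15.5%.

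| Share aged 4-5 | Gap (years) | r | Shift (SD) | Rejects, n = 100 per group | Rejects, n = 50 per group |
|---|---|---|---|---|---|
| 13.3% | 1.0 | 0.1 | 0.023-0.027 | 5.3-5.4% | 5.1-5.2% |
| 13.3% | 1.0 | 0.3 | 0.069-0.080 | 7.8-8.7% | 6.4-6.8% |
| 13.3% | 1.0 | 0.5 | 0.115-0.133 | 12.8-15.5% | 8.8-10.1% |
| 5% | 0.375 | 0.1-0.5 | 0.01-0.05 | 5.0-6.4% | not tabulated |
| 2% | 0.15 | 0.1-0.5 | 0.004-0.02 | 5.0-5.2% | not tabulated |

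Across the 13.3% rows the AUC under no true effect runs from 0.507 to 0.538.

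**Sensitivity to the assumptions.** Treating the limits as exact (uniform on 4-18 and on 6-18) gives mean ages of 11 and 12 and a share of 2/14 = 14%. With the control SD of 12/√12 = 3.46 and a normal approximation, the shift is 0.03-0.14 SD and the rejection rate 5.5-17.5% at 100 per group. The shift does not shrink as the sample grows, so the rejection rate rises: 6.0-30.3% at 200 per group.

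**Do the remedies work?** In simulation (8,000 runs per setting; the shares and correlations above; n = 100, plus n = 50 at 13.3%), the unadjusted t-test rejected 5.0-14.9% of the time, a linear model adjusted for age 4.5-5.2%, and a t-test restricted to age 6 and over 4.7-5.4%. Restriction alone suffices there only because the age mix above 6 was set equal.

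**Cost of restriction.** Losing 2 to 13 of 100 cases multiplies the standard error by √((1/98 + 1/100)/(2/100)) = 1.005 to √((1/87 + 1/100)/(2/100)) = 1.037.

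**The case against.** - **The effect may be trivial.** If only 2-5% of cases are aged 4-5, the error rate hardly moves. The upper figures need an even age spread and r = 0.5 together, and the document supports neither. This stands as a limit on size. It does not make the ranges comparable or supply a reference group at ages 4-5.
- **Age matching may be in an unseen protocol.** This is fair for balance within 6-18, where silence in this document is not counted as an error. It does not reach the floors: no matching scheme can supply a control aged 4-5 under the stated criterion.
- **The ROC comparator is not stated.** Section 1.2.2 mentions only attack and inter-episode samples, and 2.1.4(3) names no comparison group. Healthy controls are the natural reading of a diagnostic index for migraine, but for the ROC this is an inference.
- **Logistic regression might include age.** Possibly, since age is among the items collected. It would still leave the stated t-test and AUC unadjusted.
- **The mismatch is one digit and could be a text-reading error.** It cannot be excluded, as other words in the section are misread. The sponsor can settle it at once when reconciling the two lines.
- **Sex and BMI do not follow from an age-floor mismatch.** Correct. They are optional, and the point does not depend on them.

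**Conclusion.** The concern holds. The two age ranges differ in the current text, and nothing in the stated t-test or ROC analysis compensates. That part is certain from the document, apart from the inferred ROC comparator.

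The size is not certain. At 50-100 per group the effect of the floor alone runs from negligible (2% of cases aged 4-5) to modest (13%, with r up to 0.5). It would be larger with a bigger sample, a higher share of very young cases, or age mixes that also differ within 6-18. It would vanish for a metabolite unrelated to age. Because correction costs so little, this should be fixed, but it does not invalidate the study.

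**What to change.** 1. **Section 2.1.1:** reconcile the two age ranges. If recruitment is finished, restrict the case-control and ROC analyses to 6-18 years and describe cases aged 4-5 separately.
2. **Sections 1.2.1 and 2.1.4(2):** make the metabolite comparison a linear model of metabolite on group, adjusted for age and, as a routine addition, sex. Add BMI only if height and weight are recorded in controls. Keep the t-test as an unadjusted secondary result. Equal limits do not guarantee equal age distributions, so the adjustment is worth having even after restriction.
3. **Sections 1.2.2 and 2.1.4(3):** state the comparison group, and report an age-adjusted or age-stratified ROC beside the unadjusted one.

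**Cost.** SAP wording and one eligibility line. First confirm that age and sex are recorded for controls. The list of personal data in 2.1.2 belongs to a statement about patients ("blood samples were collected from all enrolled headache patients"), and 2.1.3 says only that "basic information about the children and headache characteristics" were obtained after recruiting both groups. The downside is that cases aged 4-5 leave the comparison: about 2-13 per 100 cases in the illustration, widening the standard error by 0.5-4%.

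### If the migraine types compared by one-way ANOVA are the three listed at entry, the comparison cannot separate aura from chronicity; two factors would

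*SAP*

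**What the plan says.** Section 2.1.1, case item (2), admits children who "Meet the diagnostic criteria of ICHD-3 with aura, without aura, and chronic migraine". No other passage of the SAP lists types of migraine.

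The comparison between types appears twice. Section 1.2.1 states that "one-way ANOVA was performed between different types of migraine", and section 2.1.4(2) that "one-way ANOVA was performed on the plasma levels of tryptophan metabolites between different types of migraine". Neither names the groups. The opening paragraph of section 2.1.4 links the test to the number of groups: ANOVA is "applied for comparison between the three groups", and the two-sample t-test "was used for comparison between two groups".

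Section 2.1.2, item ③, records "the presence of aura, aura symptoms, concomitant symptoms" for enrolled headache patients and, as a separate entry, "the frequency of the headache, the duration of each headache".

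The SAP gives no rule for assigning a child who is chronic and also has aura, and it plans no comparison of types with aura and chronicity as separate factors.

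**The concern.** Having aura and not having aura already divide all cases between them. A third class that is not defined by aura must therefore draw children from one or both of the first two. The SAP's own data collection treats aura as a separate item, so a chronic child will carry an aura entry of yes or no.

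A one-way layout with three such classes has no term for aura inside the chronic class. If the chronic class differs from the without-aura class, the analysis cannot say whether the cause is chronicity or the children with aura whom the chronic class contains. The comparison is one of the results that section 1.2.1 intends to combine when it draws conclusions on pathogenesis, so an aura effect could be reported there as an effect of chronicity.

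**Working it through.** **No plan figure to reproduce.** The SAP states no sample size, alpha, effect size or SD for this comparison. All numerical inputs below are assumptions.

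**Step 1: expected class means.** Let μ be the mean in episodic children without aura, *d* the aura effect and *c* the chronicity effect (both in SD units, additive), and *p* the share of chronic children who have aura. Suppose every chronic child is coded only as chronic.

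- Without aura: μ
- With aura: μ + *d*
- Chronic: μ + *c* + *p·d*

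Hence:

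- chronic minus without aura = *c* + *p·d*
- chronic minus with aura = *c* − (1 − *p*)·*d*
- with aura minus without aura = *d*

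With *c* = 0 the first contrast is *p·d* and the second is −(1 − *p*)·*d*. Both look like chronicity effects, and both are due to aura alone. The third contrast is still the full aura effect.

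**Step 2: size with *c* = 0** (chronic minus without aura).

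| *p* (assumed) | *d* (assumed) | *p·d* |
|---|---|---|
| 0.2 | 0.3 SD | 0.06 SD |
| 0.3 | 0.5 SD | 0.15 SD |
| 0.4 | 0.8 SD | 0.32 SD |

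At *p* = 0.3 and *d* = 0.5 the chronic minus with-aura contrast is −(0.7 × 0.5) = −0.35 SD.

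**Step 3: how often this would be declared significant.** Simulation with three equal classes, SD 1, two-sided 5% level, 3,000 runs per setting and *c* = 0. The table compares a t-test of chronic against without aura with the chronicity term of a linear model holding aura and chronicity as two main effects.

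| *n* per class | *d* | *p* | mean difference | false positive, three classes | false positive, two factors |
|---|---|---|---|---|---|
| 30 | 0.5 | 0 | 0.006 | 5.2% | 5.1% |
| 20 | 0.5 | 0.3 | 0.149 | 7.5% | 5.3% |
| 30 | 0.5 | 0.3 | 0.149 | 8.8% | 4.2% |
| 60 | 0.5 | 0.3 | 0.150 | 12.8% | 5.2% |
| 30 | 0.8 | 0.3 | 0.245 | 14.9% | 5.2% |
| 60 | 0.8 | 0.3 | 0.240 | 24.5% | 5.0% |
| 30 | 0.8 | 0.5 | 0.403 | 31.8% | 5.0% |

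The simulated differences agree with *p·d*. With *p* = 0 there is no bias. The last row lies outside the 20-40% range used in step 2 and shows how the error grows with the aura share. In every setting shown the two-factor model stays close to the nominal 5%.

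**The case against.** The strongest objection is that the premise is inferred. The list in section 2.1.1 is an eligibility criterion, and admissible diagnoses need not be mutually exclusive. The ANOVA sentences do not name their groups. The three groups in the opening of section 2.1.4 could be the attack, inter-attack and healthy control groups of section 2.1.3. This stands, and it is why the point is conditional. It does not remove the point: a comparison between types of migraine cannot include healthy controls, and the SAP offers no other list of types.

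A second objection is that section 2.1.1 leaves diagnosis to ICHD-3, which may assign a chronic child with aura to one class only. The documents do not show its coding rules, so a reader who infers that such a child must fall into two ANOVA classes goes further than they allow. The working above already assumes one class per child, and the mixture remains.

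Third, the SAP plans no pairwise contrasts, and if aura shifts a metabolite the overall F test is right to find that the types differ. That is correct. The difficulty lies in attributing the difference, because a reader of three class means will compare the chronic class with the others.

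Three further inferences are tempting and are not supported:

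- **That moving aura children into the chronic class dilutes the aura effect.** Under that coding the with-aura class still holds only aura children and the without-aura class only children without aura, so their contrast remains *d*. The loss is in precision.
- **That the sentence "correlation analyses were performed between the frequency, duration, severity and two types of migraine attacks" contradicts the three entry types.** The two types are undefined and may mean attack versus inter-attack, or with versus without aura.
- **That relating frequency to type is true by definition.** This would need chronic to be one of those two types, which the text does not say.

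**Conclusion.** The point holds in conditional form. If the ANOVA groups are the three types listed at entry, which is the natural reading but not a stated one, the comparison mixes aura with chronicity, and coding each child to one class does not cure this. With no chronicity effect, the chronic class would still differ from the without-aura class by *p·d*: 0.06-0.32 SD for an assumed aura share of 20-40% and an assumed aura effect of 0.3-0.8 SD, and 0.15 SD at the middle values. At those middle values the false-positive rate for that contrast is only moderately raised, at 7.5-12.8% for 20-60 children per class. It becomes large only with a stronger aura effect or a higher aura share. If no chronic child has aura, or aura does not affect the metabolite, there is no bias. The SAP neither states nor ensures either condition.

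A reader might take this as a threat to the main results. It is not: the comparison of migraine patients with healthy controls and the ROC analyses do not use the type classification. This is an inexpensive improvement to one exploratory comparison.

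**What to change.** In sections 1.2.1 and 2.1.4(2), replace the one-way ANOVA on type with a linear model for each metabolite that has two main effects:

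- aura (yes/no), from section 2.1.2 item ③
- chronic versus episodic, from the ICHD-3 diagnosis made at entry

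Report the two adjusted differences with confidence intervals, and tabulate the number of children in each of the four aura-by-chronicity cells.

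The cost is a change of SAP wording and one more term in the model. No new data are needed, and SPSS fits such a model. The downside is that the chronic-with-aura cell may be small, so an interaction may not be estimable. The main-effects model then assumes that the aura effect is the same in chronic and episodic children, and the SAP should say so.
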